6 RANDOMIZATION AND BLINDING

6.1 Randomization

Study participants will be enrolled in cohorts (blocks) of 16 dyads and randomly allocated to the immediate start intervention group ($n=8/\text{cohort}$) or the delayed start control group ($n=8/\text{cohort}$). The randomization sequence will be generated in advance by the data manager using a random number generator on a computer and will be stored separately and securely. Research staff will be unaware of the randomization sequence.

6.2 Blinding

Because we are using a delayed start control group, it will not be possible to blind participants living with memory loss or their caregivers to their group assignment. However, research staff who collect outcome data and the study statistician will be blinded to group assignment. Every effort will be made to ensure that blinding is maintained including:

- Maintaining the group assignment list separately from other study documentation.
- Having outcomes assessors remind study participants not to discuss any aspect of the study or ask any questions related to the study prior to scheduling or performing assessments.
- Randomly labeling intervention arms as Group A and Group B for the study statistician.
- Excluding assessors from staff meetings that discuss details of the intervention.
- Restricting access to the intervention section of the database to authorized personnel.

If unblinding occurs, the following will be recorded:

- The ID(s) of the unblinded participant
- The reason for unblinding

- The study staff person responsible for unblinding
- A list of person(s) who have been unblinded

Future assessments will be performed by team members who remain blinded.

7 STUDY INTERVENTIONS

7.1 Schedule of Intervention Procedures

The Moving Together Intervention includes an Initial Contact call; Home Set-up and Goals Assessment videoconference; two-way livestreaming online group classes offered for 1 hour, 2 days/week for 12 weeks; Monthly Check-Ins; PLIÉ Experience surveys (administered monthly when participants are taking classes); and a Final Evaluation survey. Each step is described in more detail below. The Schedule of Intervention Procedures in the immediate and delayed start groups is shown in the Table below.

The Intervention Team consists of trained Moving Together Instructors/Coaches and a Community Support Coordinator who will work together to accomplish the intervention tasks. In general, the instructor will perform the goals assessment and teach the Moving Together classes, which will consist of verbal instructions, demonstrations, discussions of program themes, and brief explanations for the movements and goals of the program; the community manager will provide technology support and will administer the check-ins and class surveys.

Intervention	Week 0	Weeks 1-11	Week 12	Weeks 13-23	Week 24
Initial Contact	Both groups				
Home Set-Up and Goals Assessment	Immediate start group		Delayed start group		
Moving Together Classes		Immediate start group		Delayed start group	
Monthly Check-Ins		Both groups (weeks 4, 8, 12, 16, 20, 24)			
MOVING Together Class Experience Surveys		Immediate start group (weeks 2, 6, 12)		Delayed start group (weeks 14, 18, 24)	
Final Evaluation Survey			Immediate start group		Delayed start group

7.2 Description of Intervention Procedures

7.2.1 Initial Contact

After study participants complete their consent (V0) and baseline (V1) visits and are randomized to the immediate or delayed start groups, they will be contacted by a member of the Intervention Team to let them know when their classes will begin and next steps. For participants randomly allocated to the immediate start group, the next step is to prepare for the first class by completing the Home Set-up and Goals Assessment. For

participants randomly allocated to the delayed start group, the next step is the first Monthly Check-In.

7.2.2 Home Set-Up and Goals Assessment

Before the first class, the Community Support Coordinator will determine the dyad's technology requirements to access the class videoconference portal, based on the technology information collected during telephone screening and the initial contact. Materials to enable the dyad's technology to access the class video portal including adapters or cords will be mailed if necessary, in addition to a Setup Guide and Participant Handbook in preparation for the first class.

The Instructor will then help the dyad through the Home Set-Up process to create a safe environment for the classes and will conduct the Goals Assessment to learn about each participants' personal goals, motivations and challenges. The Goals Assessment interview questions will ask about their background, interests and hobbies, including musical preferences; physical challenges; and what they hope to gain from participating in the program, potential barriers and strategies to overcome them. This information will be used to tailor the program to optimally meet the needs of each dyad. The Instructor will remind the dyad of the class days and times, and the Community Support Coordinator will email class details, online class access instructions, and contact information.

7.2.3 Moving Together Classes

The Moving Together class principles are based on those from the in-person PLIÉ and Paired PLIÉ program. The program will focus on the following Moving Together guiding principles, themes and goals:

7 Guiding Principles	12 Themes	Goal
Repetition with variation	Repetition builds muscle memory	Promote procedural learning
Progressive functional movement	Principles of functional movement	Improve daily function
Slow pace and step-by-step instruction	Go slow; Patience, respect & dignity	Minimize cognitive demands
Participant-centered goal orientation	Know your goals The power of touch	Enhance personal meaningfulness of movements
Body awareness, mindfulness and breathing	Sense and breathe Creating a learning environment	Encourage present-centeredness
Social interaction	Social engagement & emotional connection; Community	Promote meaningful connection
Positive emotions	Enjoy and explore; Music	Promote feelings of well-being

The Instructor will conduct the online livestreaming Moving Together class with the Community Support Coordinator assisting the participants through the class video platform and by phone if necessary before, during and after the class to ensure the participant's successful access to the class video platform and their class participation.

Each Moving Together class will begin with greetings and a brief check-in, to ensure that everyone feels welcomed and acknowledged. Next participants will engage in seated, mindful body awareness movements that involve massaging or tapping all major body parts (including hands, arms, thighs, calves, ankles/feet, belly, back, neck and head) and deep breathing movements (raising arms overhead while inhaling and vocalizing while exhaling). The goal of these movement sequences is to bring participants into awareness of their bodies and breathing in the present moment, and to create a calming ritual that is repeated at the beginning and end of each class. These movements are designed to be relaxing and engaging at the same time. Next participants will engage in a series of seated, standing and/or paired movements (i.e., performed with their partner) that focus on increasing capacity to perform movements that are most needed for daily function, such as increasing range of motion, reaching, turning, transitioning smoothly between sitting and standing, and balancing while standing and walking. These movement sequences will build slowly in complexity over the course of the program, depending on the functional ability levels of each class. Whenever possible, we will strive to group dyads with similar levels of physical or cognitive abilities. Finally, each class will end with repetition of the mindful body awareness and breathing movements and an invitation for participants to share what makes them feel grateful, appreciative, joyful or happy. The goal in this section of the program is to facilitate positive emotions and feelings of social connection.

Over the Intervention period of 12 weeks/24 classes, the Moving Together program will gradually and methodically progress participants through safe, functional movement sequences from simple to more complex while deepening self-awareness and mindfulness skills and building social engagement and connection through the Moving Together online video class portal.

The Instructor will adapt the program based on feedback and observations during class, Monthly Check-In data, and Moving Together Class Experience survey responses.

The final day of class will include a graduation. Participants will receive a graduation certificate in the mail prior to that day.

The Instructor and Community Support Coordinator will document class attendance and class content. Class reports during team meetings, class documentation and class video recordings will be reviewed regularly by senior team members for program fidelity.

7.2.4 Monthly Check-Ins

Monthly check-ins surveys will be sent to caregivers in both groups by email to assess for adverse events and co-interventions in both groups. Surveys may also be completed by phone, text, or paper if preferred.

We will identify adverse events by asking about hospitalizations, emergency department visits, falls, and other unexpected major medical events or changes in health status for both the CG and the PWML. If any adverse events are reported, the Community Support Coordinator will follow-up to gather more

information and will enter the information into the Adverse Event log. The procedures for reporting Serious Adverse Events and Unexpected Problems are described in detail in section 8.

In addition, we will assess for co-interventions (other life events that could potentially impact study outcomes) by asking CGs if they or PWML have started any new programs to improve their health or well-being, or whether there have been any changes to their home environment.

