5.2.4 Monthly Check-Ins (C1, C2, C3, C4, C5, C6)

Monthly check-ins will be performed with caregivers in both groups throughout the 24-week study period. The goals of the check-ins are to: a) assess for adverse events, including hospitalizations, emergency department visits, and falls; b) assess for co-interventions that could impact our study outcomes; and c) maintain contact and interest in the waitlist control group. Check-ins may be performed by email, telephone, text, or online survey.

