8 SAFETY ASSESSMENTS

8.1 Potential Risks and Benefits

Potential Risks:

- Movements may cause muscle strain, soreness, dizziness, or other injuries.
- Movements that involve standing may increase the risk of falling, although instructors work closely with participants to minimize this risk (for example, by having those with balance issues hold on to chairs for stability).
- Some participants may be frustrated by using new technology.
- Some participants may be concerned about loss of privacy associated with video-conferencing and video-recording.

Potential Benefits:

- Study participants may benefit directly by experiencing improved quality of life, better mobility, lower stress, or less social isolation.
- Study participants may increase their knowledge about ways to improve quality of life for people living with memory loss.

- Study participants may feel that they are helping others by contributing to knowledge about memory loss and caregiving.

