8.2 Adverse Events (AEs) and Serious Adverse Events (SAEs)

Study participants will be monitored for adverse events (AEs) during livestreaming classes by Moving Together coaches. Prior to the first class, instructors will create a list of class participants that is easily accessible and includes their names, phone numbers, addresses, emergency contact information, and local 10-digit emergency center number in case of potential AEs during class. If there is an emergency, the instructor will stop class, contact the Community Support Coordinator/PI, and call the local emergency center.

In addition, we will elicit information about AEs including falls and healthcare utilization in all study participants during monthly check-ins. All AEs will be tracked in a research study database that will include:

- Dyad PIDN
- Person affected (PWML or CG)
- Date of occurrence
- Date of first awareness
- Brief description of AE
- Initial determination of whether the event was study-related (definitely, possibly, unrelated)
- Initial determination of whether the event was serious or unexpected (yes/no)
- Whether the event is reportable (yes/no)
- If yes:
 - Date reported to SO
 - Date reported to NIA PO
 - Date reported to UCSF IRB
- Comments

Definitions are provided below.

Adverse event (AE):

Any negative medical occurrence in a research study participant that is temporally associated with their participation in the research, whether or not considered related to participation in the research.

Serious adverse events (SAEs):

Any AE that:

- Results in death
- Is life-threatening, or places the participant at immediate risk of death from the event as it occurred
- Requires or prolongs hospitalization
- Causes persistent or significant disability or incapacity
- Requires medical or surgical intervention to prevent an outcome listed above
- Changes the risk/benefit ratio

Unanticipated Problems (UPs):

- Unexpected, in terms of nature, severity, or frequency given (a) the research procedures described in the study protocol and informed consent documents and (b) the characteristics of the study population
- Definitely or possibly related to participation in the research
- Suggests that the research places participants or others at a greater risk of harm (including physical, psychological, economic, or social harm) than was previously known or recognized

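### No described question asks specifically about muscle strain, soreness or dizziness, so minor programme-related harms after class are likely to be under-ascertained and are not collected alike in the two arms

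*Combined protocol and SAP*

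**What the plan says.** **Risks.** The first entry under potential risks in section 8.1 reads: "Movements may cause muscle strain, soreness, dizziness, or other injuries". Falls are the second entry.

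**Definition.** Section 8.2 defines an adverse event as "Any negative medical occurrence in a research study participant that is temporally associated with their participation in the research". Relatedness to the study is not required, and there is no severity threshold.

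**Monthly check-in.** Section 5.2.4 gives one goal of the check-ins as to "assess for adverse events, including hospitalizations, emergency department visits, and falls". Section 7.2.4 is more specific about the content: "We will identify adverse events by asking about hospitalizations, emergency department visits, falls, and other unexpected major medical events or changes in health status". The question covers each dyad member, the caregiver and the person with memory loss (PWML). On the respondent it says: "Monthly check-ins surveys will be sent to caregivers in both groups by email". The schedule in section 7.1 places check-ins at weeks 4, 8, 12, 16, 20 and 24. Section 8.2 describes the same check-ins more loosely: "we will elicit information about AEs including falls and healthcare utilization in all study participants during monthly check-ins".

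**In class.** Section 8.2 adds: "Study participants will be monitored for adverse events (AEs) during livestreaming classes by Moving Together coaches".

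**The concern.** The question that is meant to find adverse events is worded more narrowly than the protocol's own definition of one, and the gap falls on the harms that the protocol expects from the movements. A risk that is already listed is hard to call unexpected, and soreness or strain is usually not a major medical event. A caregiver reading the prompt as section 7.2.4 words it could reasonably leave these out.

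For a movement programme, minor musculoskeletal complaints and dizziness are much of the tolerability information. Section 8.2 requires each logged event to be graded for relatedness, but an event must first be elicited. Section 7.2.3 also says that the instructor adapts the programme partly on check-in data, and that feedback is weaker if these complaints are not prompted.

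**Working it through.** No arithmetic decides this point. The check sets each described route for collecting adverse events beside the harms in the first risk entry of section 8.1.

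| Route | Section | Who is covered in weeks 1-12 | Names strain, soreness, dizziness or injury? |
|---|---|---|---|
| Monthly check-in | 5.2.4, 7.2.4, 8.2 | Both arms, by caregiver report | No. Names hospitalizations, emergency visits and falls, then a general phrase |
| Coach observation | 8.2 | Immediate start only, during class | No question described |
| Brief check-in opening each class | 7.2.3 | Immediate start only | No. Its stated purpose is welcome |
| Class experience scale | 5.2.5 | Immediate start only | No. Six items on feelings in class |
| Final evaluation | 5.2.6 | Immediate start only, after the last class | No. Open-ended questions on changes observed |

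**Reading the general phrase.** The end of the section 7.2.4 prompt can be read in two ways.
1. If the words meaning unexpected and major govern the whole phrase, an ordinary strain or spell of soreness falls outside it.
2. If the reference to health status stands alone, new or persistent pain or dizziness could fall inside it.

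The grammar does not settle which is meant. Under either reading the listed harms are not named.

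**Recall interval.** Classes run 2 days a week, so 2 x 4 = 8 classes fall between successive check-ins, and 2 x 12 = 24 over the programme. The caregiver reports for both members of the dyad over that interval.

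**Comparability.** Three of the six check-ins (weeks 4, 8 and 12) fall in the randomised comparison period and apply to both arms. The other four routes in the table reach only the immediate-start arm in that period. A count of minor events by arm would therefore mix two levels of observation. Extra observation raises the count in the arm taking classes, while the absence of a specific question lowers it in both. The net direction of the distortion is unknown.

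**Size.** The protocol gives no expected frequency of strain, soreness or dizziness, so no figure for missed events can be derived. The population exposed is up to 224 x 2 = 448 people.

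**The case against.** A reader might go further and infer that these harms are not asked about at all, that they would go unreported, and that the trial would show a clean record only because it never asked. The documents do not support that.

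- The reference to changes in health status may be a separate and broader prompt.
- Sections 5.2.4 and 8.2 both introduce their lists as non-exhaustive.
- Section 7.2.4 summarises the survey, and the form itself is not among the documents. The list of protocol changes records that an open-ended question was added to the check-in survey. Its topic is not given, so it neither proves capture nor can be ignored.
- Participants meet staff twice a week while in classes, and the coordinator may help by phone around classes (section 7.2.3). Soreness that appears hours later can be mentioned at the next class.

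A reader might also infer that harm leading a dyad to stop classes would be missed. Attendance is documented (section 7.2.3), check-ins continue for 24 weeks (section 5.2.4), and follow-up continues with permission after stopping (section 9). No described field records why classes were stopped, but missed capture is not shown.

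On importance, section 8.3 calls the study relatively low risk, and section 4.2 excludes physical limitations, such as chronic pain or vertigo, that could affect participation. The SF-12 covers caregiver bodily pain, and PWML mobility is measured at follow-up in both arms. Falls and health service use, the named exploratory outcomes, are asked about directly.

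All of this stands as a limit on the claim. It does not supply a targeted question: each alternative route relies on someone volunteering the complaint, and the quality-of-life and mobility scales are not adverse-event records.

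**Conclusion.** The point holds in a limited form. No described question asks specifically about the harms that section 8.1 lists first, the section 7.2.4 wording is narrower than the section 8.2 definition, and minor harms arising after class are likely to be under-ascertained. In weeks 1-12 they are also not collected alike in the two arms. The shortfall cannot be sized from the documents.

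The conclusion assumes that section 7.2.4 fairly summarises the survey form. If the form already names these harms, what remains is to say so in the protocol. The primary and secondary outcome analyses do not depend on minor adverse-event counts. This is a cheap improvement in harm reporting, not a threat to the main result.

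**What to change.** Align sections 5.2.4(a) and 7.2.4 with the section 8.2 definition by adding one item to the existing monthly check-in, asked in both arms and separately for the PWML and the caregiver:

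- any new muscle strain, soreness, dizziness or other injury since the last check-in (yes or no);
- the date;
- whether it needed care or limited activity.

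Tabulate the answers for weeks 1-12 by randomised arm. List class-observed events separately, since only the immediate-start arm can contribute them in that period. No time-from-class window is proposed: the documents give no basis for one, and it could not apply to controls in weeks 1-12.

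**Cost.** IRB approval of the revised form and more non-serious entries for the coordinator to follow up and log. No new visit is needed. The answers would still rest on four-week recall by caregivers who know their group, so the between-arm table should be read with that limit stated. The change concerns what is asked and recorded, not how any event is managed.

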7.2.5 Moving Together Class Experience Surveys

The Community Support Coordinator will ask participants to complete the Moving Together Class Experience surveys immediately after class during weeks 2, 6, and 12 (immediate start group) and weeks 14, 18, and 24 in the delayed start group. PWML and CGs will be asked to answer separately. The goal of these surveys is to gather information in ‘real time’ to assess participant experience.

7.2.6 Final Evaluation Survey

After the final class, the Community Support Coordinator will ask participants to complete the Final Evaluation survey. PWML and CGs will be asked to answer separately. The goal of these surveys is to gather information about participant satisfaction and qualitative observations.

7.2.7 Delayed Start Control

The delayed start control group will be encouraged to continue with their usual daily activities while they wait for their classes to begin.

8 SAFETY ASSESSMENTS

8.1 Potential Risks and Benefits

Potential Risks:

- Movements may cause muscle strain, soreness, dizziness, or other injuries.
- Movements that involve standing may increase the risk of falling, although instructors work closely with participants to minimize this risk (for example, by having those with balance issues hold on to chairs for stability).
- Some participants may be frustrated by using new technology.
- Some participants may be concerned about loss of privacy associated with video-conferencing and video-recording.

Potential Benefits:

- Study participants may benefit directly by experiencing improved quality of life, better mobility, lower stress, or less social isolation.
- Study participants may increase their knowledge about ways to improve quality of life for people living with memory loss.

- Study participants may feel that they are helping others by contributing to knowledge about memory loss and caregiving.

